- [23] History of clinically significant multiple or severe drug allergies, significant atopy, or severe posttreatment hypersensitivity reactions (including but not limited to erythema multiforme major, linear immunoglobulin A dermatosis, toxic epidermal necrolysis, and/or exfoliative dermatitis).

Imaging, Vital Signs, Electrocardiograms, Laboratory Tests, and Physical Examination

- [24] Have any clinically important abnormality at screening, as determined by the investigator, in physical or neurological examination, vital signs, ECG, or clinical laboratory test results that could be detrimental to the participant, could compromise the study, or show evidence of other etiologies for dementia.
- [25] Screening MRI that shows evidence of significant abnormality that would suggest another potential etiology for progressive dementia or a clinically significant finding that may impact the participant's ability to safely participate in the study.
- [26] Have any contraindications for MRI, including claustrophobia or the presence of contraindicated metal (ferromagnetic) implants/cardiac pacemaker.
- [27] Sensitivity to flortaucipir F18.
- [28] Contraindication to PET and present or planned exposure to ionizing radiation that, in combination with the planned administration of study PET ligands, would result in a cumulative exposure that exceeds local recommended exposure limits.
- [29] Cardiovascular screening ECG criteria
- heart rate less than 45 beats/min
 - Mobitz type 2 second-degree or third-degree AV block (uncorrected by cardiac pacemaker), and
 - ECG with QTc >450 msec in males and >470 msec in females.
- [30] Calculated creatinine clearance <30 mL/min (Cockcroft–Gault formula; Cockcroft and Gault 1976) at screening.
- [31] ALT $\geq 2\times$ the ULN of the performing laboratory, AST $\geq 2\times$ ULN, TBL $\geq 2\times$ ULN, or ALP $\geq 2\times$ ULN at screening.

NOTE: Participants with TBL $\geq 2\times$ ULN are not excluded if they meet all of the following criteria for Gilbert syndrome:

- a. bilirubin is predominantly indirect (unconjugated) at screening (direct bilirubin within normal limits).
- b. absence of liver disease.
- c. ALT, AST, and ALP $\leq 1\times$ ULN at screening.
- d. hemoglobin is not significantly decreased at screening.

Prior/Concomitant Therapy (Refer to Manual of Operations for complete lists)

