8.2.6. Hepatic Safety Monitoring

Close Hepatic Monitoring

Laboratory tests (Section 10.4), including ALT, AST, ALP, TBL, direct bilirubin, gamma-glutamyl transferase, and creatine kinase, should be repeated within 48 to 72 h to confirm the abnormality and to determine if it is increasing or decreasing, if 1 or more of these conditions occur:

If a participant with baseline results of ...	develops the following elevations:
ALT or AST <1.5x ULN	ALT or AST ≥3x ULN
ALP <1.5x ULN	ALP ≥2x ULN
TBL <1.5x ULN	TBL ≥2x ULN (except for participants with Gilbert's syndrome)
ALT or AST ≥1.5x ULN	ALT or AST ≥2x baseline
ALP ≥1.5x ULN	ALP ≥2x baseline
TBL ≥1.5x ULN	TBL ≥2x baseline (except for participants with Gilbert's syndrome)

Abbreviations: ALP = alkaline phosphatase; ALT = alanine aminotransferase; AST = aspartate aminotransferase; TBL = total bilirubin level; ULN = upper limit of normal.

If the abnormality persists or worsens, clinical and laboratory monitoring, and evaluation for possible causes of abnormal liver tests should be initiated by the investigator in consultation with the Lilly-designated Medical Monitor. At a minimum, this evaluation should include physical examination and a thorough medical history, including symptoms, recent illnesses (e.g., heart failure, systemic infection, hypotension, or seizures), recent travel, history of concomitant medications (including over-the-counter), herbal and dietary supplements, and history of alcohol drinking and other substance abuse.

Initially, monitoring of symptoms and hepatic biochemical tests should be done at a frequency of 1 to 3 times weekly, based on the participant's clinical condition and hepatic biochemical tests. Subsequently, the frequency of monitoring may be lowered to once every 1 to 2 weeks, if the participant's clinical condition and laboratory results stabilize. Monitoring of ALT, AST, ALP, and TBL should continue until levels normalize or return to approximate baseline levels.

Comprehensive Hepatic Evaluation

A comprehensive evaluation should be performed to search for possible causes of liver injury if 1 or more of these conditions occur:

If a participant with baseline results of...	develops the following elevations:
ALT or AST <1.5x ULN	ALT or AST ≥3x ULN with hepatic signs/symptoms*, or ALT or AST ≥5x ULN
ALP <1.5x ULN	ALP ≥3x ULN
TBL <1.5x ULN	TBL ≥2x ULN (except for participants with Gilbert's syndrome)

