Bretz's graphical approach will be utilized to provide strong control of the study-wise Type I error rate for the primary and secondary hypotheses of clinical efficacy endpoints at an alpha level of 0.05 (Bretz et al. 2009, 2011). Details on the graphical approach and testing strategy will be specified in Section 4.9.2.1.

If any of the individual items for ADAS-Cog₁₃ or ADCS-ADL or CDR-SB are missing or unknown, every effort will be made to obtain the score for the missing item or items. If either ADAS-Cog₁₃ or ADCS-iADL is missing, iADRS score will be considered missing. For all other scales, if any item is missing, any total or sum involving that item will be considered missing. For all scales, if a limited number of individual test items are missing, imputation using prorating will be implemented to obtain a total score.

A database lock is expected to occur after all randomized participants have had a chance to complete their final study visit in the double-blind period of the study (Period 2a/2b). Efficacy and safety analyses will be conducted based on data collected during the double-blind period. Visit 801 is the safety follow-up visit where concomitant medications, AEs, physical evaluation (e.g., vital signs, ECG, etc.), laboratory tests, and C-SSRS are collected. Data collected at the safety follow-up visit (V801) during Study Period 3 and throughout Study Period 4 (Post-treatment Safety Follow-up Period) will be combined for analysis unless otherwise specified.

Any change to the data analysis methods described in the protocol will require an amendment only if it changes a principal feature of the protocol. Any other change to the data analysis methods described in the protocol and the justification for making the change will be described in the SAP and the clinical study report (CSR). Additional exploratory analyses of the data will be conducted as deemed appropriate.

Table 4.1. Baseline Definition for Safety Groups

Analysis Type	Baseline
1.1) Treatment-Emergent Adverse Events	The baseline period is defined as the start of screening and ends prior to the first dose of study treatment (typically at Week 0).
1.2) Treatment-Emergent Abnormal Labs, Vital Signs, and ECGs.	Baseline will be all scheduled and unscheduled measurements recorded during the baseline period as defined above (1.1).

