Treatment differences in the proportion of participants with treatment-emergent high or treatment-emergent low or treatment-emergent abnormal laboratory values at (1) anytime and (2) each postbaseline visit will be assessed using Fisher's Exact test. Treatment-emergent high or low laboratory abnormality will be based on SI unit. For each laboratory analyte, only participants who were low or normal at all baseline assessments and have at least 1 postbaseline will be included in the denominator when computing the proportion of participant with treatment-emergent high. Similarly, only participants who were high or normal at all baseline assessments and have at least 1 postbaseline will be included in the denominator when computing the proportion of participant with treatment-emergent low. In addition, treatment differences in the proportion of participants who have normal baselines with a change to abnormal high or abnormal low values at any postbaseline visits will be summarized.

For urinalysis parameters, baseline to postbaseline shifts will be summarized at each visit. Likelihood ratio chi-square tests will be used to compare increase, no change, and decrease shifts in urinalysis parameters between treatment groups at each visit.

For hormone panel parameters (i.e., follicle-stimulating hormone (FSH), luteinizing hormone (LH), Inhibin B, Testosterone, Estrogen), baseline to postbaseline values as well as change from baseline at each post-baseline visits will be summarized.

For all laboratory analytes, frequencies of participants with notable changes (i.e., increases or decreases of a pre-specified amount unique to each analyte) from baseline to each postbaseline visit were also summarized for all participants and stratified by low, normal, or high at baseline.

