The proportion of subjects with treatment-emergent clinically significant changes from a low value or normal value at all baselines at any time in alanine aminotransferase (ALT), alkaline phosphatase (ALP), and total bilirubin will be summarized by treatment group. Clinically significant changes of interest for hepatic laboratory values at any time are: ALT or AST ≥ 3 x upper limit of normal (ULN), total bilirubin ≥ 2 x ULN, ALP ≥ 2 x ULN, ALT ≥ 5 x ULN, ALT ≥ 10 x ULN, and total bilirubin ≥ 2 x ULN. Additionally, Hy's Law analysis will be conducted by comparing treatment groups with regard to the proportion of participants with (ALT ≥ 3 x ULN OR AST ≥ 3 x ULN) AND total bilirubin ≥ 2 x ULN. Comparisons between treatment groups will be carried out using Fisher's Exact test. When criteria are met for hepatic evaluation and completion of the hepatic safety case report form (CRF), investigators are required to answer a list of questions pertaining to the participant's history, relevant preexisting medical conditions, and other possible causes of liver injury. A listing of the information collected on the hepatic safety CRF will be generated.

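### The hepatic x-ULN proportions in SAP 4.10.4 leave out enrolled participants whose ALT, ALP or bilirubin was above normal at any baseline, so rare severe elevations can be missing from the threshold table

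*SAP*

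**What the plan says.** SAP 4.10.4 plans a hepatic summary by treatment group of "treatment-emergent clinically significant changes from a low value or normal value at all baselines at any time", naming ALT, ALP and total bilirubin. The next sentence gives the cut-offs. "Clinically significant changes of interest for hepatic laboratory values at any time are": ALT or AST ≥3x ULN, ALT ≥5x and ≥10x ULN, ALP ≥2x ULN and total bilirubin ≥2x ULN (the last is listed twice).

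The same section has a general rule for treatment-emergent high values: "only participants who were low or normal at all baseline assessments and have at least 1 postbaseline will be included in the denominator". Table 4.1 in SAP 4.1 says what baseline means for treatment-emergent laboratory abnormalities: "Baseline will be all scheduled and unscheduled measurements recorded during the baseline period".

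Two nearby analyses carry no such restriction as written:

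- A Hy's "Law analysis will be conducted by comparing treatment groups with regard to the proportion of participants with" ALT or AST ≥3x ULN together with total bilirubin ≥2x ULN.
- Notable changes, described as "increases or decreases of a pre-specified amount unique to each analyte", are summarized for everyone and by baseline status. The amounts are not given.

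Protocol 5.2, criterion 31, excludes at screening an ALT of 2x "the ULN of the performing laboratory" or more. The same multiple applies to AST, total bilirubin and ALP. Participants who meet the listed criteria for Gilbert syndrome may enroll with bilirubin at or above 2x ULN.

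**The concern.** The eligibility rule and the table filter use different limits. The protocol admits people whose liver tests are above ULN but below 2x ULN. The hepatic table counts only those who were never above ULN before dosing. A large multiple-of-ULN rise is of interest whatever the starting value, and severe rises are rare enough that one or two cases per arm can change how a table of about 110 per arm is read. If such a case occurs in someone with a mildly raised baseline, the by-arm proportions and the Fisher comparison for the ALT ≥5x and ≥10x, ALP ≥2x and bilirubin ≥2x categories will not include it.

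**Working it through.** The documents give no count or rate of raised baseline liver tests, so there is no plan figure to reproduce. The check is a reading of the text, followed by an illustration under stated assumptions.

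**1. Who is removed.** Clinical chemistry is scheduled before dosing at both Visit 1 and Visit 2 (protocol 1.3.1 and 1.3.2). Under Table 4.1 any pre-dose value counts as baseline, including unscheduled ones. One value above ULN is therefore enough to remove a participant for that analyte. Criterion 31 lets such participants in as long as the screening value is below 2x ULN.

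**2. Which rows are affected.**

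| Category in SAP 4.10.4 | Limited to low or normal at all baselines? |
|---|---|
| ALT ≥5x, ALT ≥10x ULN | Yes, ALT is named |
| ALP ≥2x ULN | Yes, ALP is named |
| Total bilirubin ≥2x ULN | Yes, bilirubin is named |
| ALT or AST ≥3x ULN | Unclear, AST is not named |
| Hy's Law | No restriction written |

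**3. Set against protocol 8.2.6.** For baseline ALT or AST below 1.5x ULN the protocol uses absolute limits: close monitoring from 3x ULN, and comprehensive evaluation from 5x ULN (or from 3x with signs or symptoms). A participant going from 1.3x to 10x ULN meets both, but is in neither the ALT ≥5x nor the ALT ≥10x row. For baseline at or above 1.5x ULN the close-monitoring trigger becomes "ALT or AST ≥2x baseline". At a baseline of exactly 1.5x ULN that equals 2 × 1.5 = 3x ULN, the SAP's lowest aminotransferase cut-off. The SAP has no table built on the baseline-relative triggers.

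**4. Rise needed to reach a cut-off** (cut-off ÷ baseline multiple):

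| Baseline (x ULN) | To 3x | To 5x | To 10x |
|---|---|---|---|
| 1.0 | 3.0-fold | 5.0-fold | 10.0-fold |
| 1.5 | 2.0-fold | 3.3-fold | 6.7-fold |
| 1.99 | 1.5-fold | 2.5-fold | 5.0-fold |

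**5. Illustration of size.** Let s be the share above ULN at any baseline for one analyte (assumed 5%, 10% or 15%). Let RR be the rate at which they reach a given cut-off relative to the others (assumed 1, 3 or 5). Take 110 per arm, as randomized.

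- Left out per arm = 110 × s
- Share of all cases left out = s·RR / (s·RR + 1 − s)
- All-participant proportion ÷ restricted proportion = 1 − s + s·RR

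| s | Left out per arm (of 330) | Denominator left per arm | Share of cases left out, RR = 1 / 3 / 5 |
|---|---|---|---|
| 5% | 5.5 (16.5) | 104.5 | 5% / 14% / 21% |
| 10% | 11 (33) | 99 | 10% / 25% / 36% |
| 15% | 16.5 (49.5) | 93.5 | 15% / 35% / 47% |

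With RR = 1 the ratio of proportions is 1 − s + s = 1, so the reported proportion does not change. At s = 10% and RR = 3 it is 0.90 + 0.30 = 1.2.

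**The case against.** The strongest reply has four parts.

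*These participants are covered elsewhere.* Hy's Law has no written baseline condition. Notable changes are summarized for all participants and by baseline status. Summary tables include the maximum, and the rank-based MMRM uses the Safety set. Listings include all visits. The hepatic safety CRF is listed when evaluation criteria are met, which the 1.3x-to-10x example does. A clinically significant result would also be reported as an AE. AESI definitions are redacted, so a further hepatic summary cannot be ruled out. This stands in part: a reader might infer that such a case disappears from the report, and it does not. But none of the visible outputs supplies an x-ULN proportion by arm for this group. The notable-change amounts are unstated, Hy's Law also needs raised bilirubin, and listings, maxima and AE tables give no threshold proportion.

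*The ≥3x row may still catch them.* This stands. Because AST is not named, someone with raised baseline ALT and normal AST could enter that row through AST. It cannot be said that such a participant is missing from every hepatic count.

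*The proportion need not fall.* This also stands. The filter removes people from numerator and denominator alike, so the proportion is understated only if raised-baseline participants cross the cut-offs more often. That is plausible, but the documents do not show it.

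*The rule is conventional.* The SAP applies similar baseline conditions to other laboratory tests and to vital signs and ECGs. That makes it consistent, but does not supply the missing counts.

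**Conclusion.** The point holds for the ALT ≥5x, ALT ≥10x, ALP ≥2x and bilirubin ≥2x ULN rows, analyte by analyte. For the ALT-or-AST ≥3x row it is open until AST handling is stated. It does not extend to Hy's Law.

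The effect is that a rare severe elevation in an eligible participant can be missing from the threshold table, though not from the study report. A reader might go further and infer that the table understates the liver finding or favours the active arms. The documents support neither reading. The filter rests on pre-dose values in a randomized trial, and no relative rate for raised-baseline participants is given.

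The number affected is unknown. The 5.5 to 16.5 per arm, and the 5% to 47% of cases left out, depend entirely on the assumed shares and relative rates. The per-arm figures count people outside a denominator, not missed elevations. This is a worthwhile and cheap correction to a safety table, and it has no bearing on the efficacy conclusions.

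**What to change.** In SAP 4.10.4:

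- Report each x-ULN category for all Safety-set participants with at least one post-baseline value for the analyte.
- Keep the present low-or-normal-at-all-baselines result as a subset row, with raised-baseline participants shown separately. Identify any Gilbert syndrome participants already at or above 2x ULN for bilirubin, since they would otherwise count without any change.
- State that AST follows the same rule as ALT, ALP and bilirubin, and delete the repeated bilirubin criterion.

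The cost is a few lines of SAP text, one changed table filter and some extra rows. The planned result survives as the subset row. The downside is that a few counted elevations will start from an already raised value, which the split by baseline status makes visible. If the double-blind data are already unblinded, the rows can still be added under the SAP 4.1 allowance for additional exploratory analyses and labelled in the CSR as a later addition.

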4.10.5. Vital Signs and Other Physical Findings

Vital sign measurements and weight will be analyzed using continuous data (change from baseline) and categorical data (proportion of potentially clinically significant changes) using the safety dataset. Summary will include data collected at scheduled visits only. Data collected at unscheduled visits will be provided in the listing.

Summary statistics will be presented for observed values at baseline and for change from baseline results at each scheduled postbaseline visit. Sitting systolic and diastolic blood pressure and pulse (measurement after 5 minutes in the sitting position), orthostatic diastolic and systolic blood pressures, and orthostatic pulse (measurement after 5 minutes in the supine position minus that after 3 minutes in the standing position), temperature, and weight by treatment group for all participants in the safety population will be summarized. If there are multiple records of vital sign or weight measurements at baseline or postbaseline visit, the last record will be used.

Measures of central tendency for vital sign and weight raw measurements and change from baseline will be summarized with boxplots. Boxplots will display results quarterly for the first 24 weeks and semi-annually for the rest of the study period (Visit 5, 8, 15, 21, 25, 29) and for the last visit (LOCF). Summary tables of N, mean, median, quartiles, min, max, standard deviation,

and p-value (for change scores) will be included. If there are considerable missing visits, the measures of central tendency may be based on MMRM analyses.

With the large number of visits at which vital signs are scheduled to be measured, the MMRM model is not suitable for the change from baseline comparison of treatments due to computational challenges. Change from baseline to each postbaseline visit at which vital signs are taken will be assessed using an ANCOVA model with treatment as an independent factor and baseline value and age as covariates in the model. This analysis will be done separately for each vital sign parameter and weight.

The incidence of treatment-emergent abnormal high or low vital signs and weight will be presented by treatment group and visit. Treatment-emergent vital sign evaluations are defined for evaluations collected after the initiation of study medication. Abnormal criteria for postbaseline vital signs and weight are presented in Appendix 1. Any vital sign or weight meeting the criteria will be considered abnormal. Treatment differences in the proportion of participants with treatment-emergent abnormal high or low vital signs and weight will be assessed between treatment groups using Fisher's Exact test at (1) any time (2) postbaseline visit. Baseline will be considered as all measurements prior to the initiation of the first dose and all baseline assessments must not meet abnormality criteria to be included in the analysis.

For each vital sign at each postbaseline visit, only participants who had a baseline result and had a non-missing result at that postbaseline visit will be included in the denominator when computing the proportion of participants with treatment-emergent high, low, or abnormal values.

Summary and analyses of change from baseline in weight will be provided. The proportion of participants with a weight gain or loss of $\geq 7\%$ of baseline body weight will be compared between treatment groups using Fisher's Exact test at each visit and at any time.

A listing of treatment-emergent abnormal vital signs and weight will also be presented.

4.10.6. Electrocardiograms

ECG measurements will be analyzed using continuous data (change from baseline) and categorical data (proportion of treatment-emergent abnormalities) using the safety dataset. Summary will include data collected at scheduled visits only. Data collected at unscheduled visits will be provided in the listing.

The ECG measurements are derived from three 10 second readings taken every 30 seconds. These 3 readings are to be averaged prior to analysis. Additionally, whenever ECG is measured in triplicate, the average of these readings will be used in the analysis. If there are multiple records after averaging ECG triplicates within a visit, the last record of averages will be used.

The analysis will be done for the following ECG measurements: heart rate, PR, QT, QTc, and RR intervals and QRS duration. All analyses of QTc will be carried out using the Fridericia correction (QTcF) method. Measures of central tendency for ECG raw measurements and change from baseline will be summarized with boxplots. Boxplots will display results quarterly for the first 24 weeks and semi-annually for the rest of the study period (Visit 5, 8, 15, 21, 25, 29) and

for the last visit (LOCF). Summary tables of N, mean, median, quartiles, min, max, standard deviation, and p-value (for change scores) will be included. If there are considerable missing visits, the measures of central tendency may be based on MMRM analyses.

Change from baseline to each postbaseline visit at which ECG measurements are taken may be assessed using an MMRM model. The model will include the fixed effects of treatment, visit as a categorical variable, and treatment-by-visit interaction as well as continuous effects of baseline ECG score and age at baseline. This analysis will be done separately for each ECG parameter.

QTc assessment based on C-QTc modeling evaluating QTc effects using MMRM may be conducted if deemed appropriate (Garnett C. et. al. 2017). The analysis model includes the fixed effects of treatment, concentration, time (nominal time), baseline QTcF as covariate, and subject and subject-by-concentration interaction as random effects. An unstructured covariance matrix will be used to model the within-subject variance-covariance of residual errors across visits. The handling of the lack of convergence with the unstructured covariance structure matrix is the same as described in Section 4.8.2.2. The Kenward-Roger approximation will be used to estimate the denominator degrees of freedom. Each dose arm effect, its relative effect to placebo on QTcF, and their corresponding 90% CI will be estimated via an appropriate linear combination of the coefficients using the geometric mean of the Cmax at the corresponding dose. Note the placebo concentration is zero. The same model may be applied to evaluate the relationship of the concentration and change from baseline in heart rate, PR interval, and QRS duration.

Incidence of treatment-emergent abnormal ECGs will be assessed by comparisons at (1) anytime and (2) each postbaseline visit between treatment groups with Fisher's Exact test. For analyses of treatment-emergent abnormal ECGs, baseline will be considered as all measurements prior to the initiation of the first dose. Abnormal ECG criteria and criteria for abnormal QTcF prolongation are presented in Appendix 2.

Treatment-emergent high ECG parameters (heart rate, PR interval, QRS duration, QT and QTcF intervals) are the values which are low or normal at all baseline visits and fall into the high abnormal categories postbaseline. Similarly, treatment-emergent low ECG parameters (heart rate, PR interval, QRS duration) are the values which are high or normal at all baseline visits and fall into the low abnormal categories above.

In addition, treatment differences in the proportion of participants who have normal baselines with a change to abnormal high or abnormal low values at any postbaseline visits will be summarized.

